### 3. RESEARCH STRATEGY

#### 3A. SIGNIFICANCE

Our objective is to maintain the cessation of intoxicated driving afforded by the Ignition Interlock Device (IID) by mobilizing the DWI offender's social network, *focusing on CFMs*, and enhancing their involvement through the use of smartphone technology. This study will be the first to use smartphone technology to extend and make permanent the cessation of intoxicated driving, providing an intervention that uses easily-accessible and diffusible technology.

#### 3A.1. DWI Interventions and Outcomes

Nochajski and Stasiewicz found that deterrence sanctions employed soon after the offense (e.g., fines, license suspension) may have a deterrent effect for repeat offense. IIDs have been shown to be effective while installed in offenders' cars; however, once removed, re-arrest rates rise to levels comparable to offenders who do not have IIDs installed. Evidence for the efficacy of therapeutic interventions for DWI offenders has improved over time. Cognitive-behavioral skills training and brief intervention modes have shown moderate effects for DWI offenders. Interventions that engage and retain the offender in treatment may produce beneficial results. Notably, family-based approaches which accomplish this are the basis of the planned smartphone app.

#### 3A.2. Family-Involved Treatment

One limitation of DWI treatment interventions is the exclusive focus on the offender. Treatments that address the social environment should result in better maintenance of change by decreasing environmental cues for drinking and providing positive incentives for desirable behaviors. Research has found that family-involved treatment enhances positive AUD outcomes and family-based contingency management improves adherence to aftercare and medication. Efficacious treatments include interventions for family members alone; contingency management where family members learn to provide desirable outcomes contingent on treatment goals; 12-20 session protocols of behavioral couple therapy (BCT); brief BCT of 1-6 sessions; and single session applications of the BCT model to any CFM that motivates persons undergoing detoxification to continue treatment. Results across this literature suggest three core treatment elements: (a) increasing family support and reinforcement for behavior change, (b) increasing positive exchanges in the family, and (c) improving communication. The proposed *B-SMART* intervention incorporates these three major elements.

#### 3A.3. Smartphone Technology in Health Communication Interventions

Smartphone applications (apps) are changing healthcare in a number of areas, including health education and clinical practice, data collection, sexual health education, weight management, diabetes, smoking cessation, substance abuse, and sun protection. To date, there are few apps related to substance abuse available. Mobile apps on smartphones have not been tested extensively for disease prevention, but have for monitoring behavior. Cell phone use is widespread. Recent Pew Internet research indicates that 77% of adults in the United States are smartphone owners. Smartphones usually accompany users are usually turned on. Thus, mobile apps can deliver advice/reminders and content to the families of DWI offenders at all times. Little research has been conducted on use of smartphones for DWI offense issues in family settings. Some DWI-related smartphone apps are available: *R-U-Buzzed* estimates BAC and warns intoxicated users not to drive; *Stumble Safely* plots safe walking routes home for intoxicated customers; *SafeRide* calls cabs for intoxicated bar customers. However, no empirical evaluations of these DWI-related smartphone apps have been reported, and all are targeted to the offender only. Smartphone apps for DWI offenders or their family members have not been reported in the research literature or popular press.

#### Preliminary Studies: DWI Research and Treatment.

Drs. [name] and [name] have extensive experience conducting DWI-related research, including randomized trials of the efficacy of MADD Victim Impact Panels on DWI Recidivism, an incarceration/ treatment program for first-time DWI offenders, and Responsible Beverage Service training. They have developed extensive research experience with DWI offenders, including successful recruitment, assessment, tracking, and data analysis. [name] directed an outpatient treatment program that served DWI offenders for 10 years and has clinical experience that complements the other investigators' research experience.

One limitation of DWI treatment interventions is the exclusive focus on the offender. Treatments that address the social environment should result in better maintenance of change by decreasing environmental cues for drinking and providing positive incentives for desirable behaviors. Research has found that family-involved treatment enhances positive AUD outcomes and family-based contingency management improves adherence to aftercare and medication. Efficacious treatments include interventions for family members alone; contingency management where family members learn to provide desirable outcomes contingent on treatment goals; 12-20 session protocols of behavioral couple therapy (BCT); brief BCT of 1-6 sessions; and single session applications of the BCT model to any CFM that motivates persons undergoing detoxification to continue treatment. Results across this literature suggest three core treatment elements: (a) increasing family support and reinforcement for behavior change, (b) increasing positive exchanges in the family, and (c) improving communication. The proposed *B-SMART* intervention incorporates these three major elements.

#### Preliminary Studies: Family-involved Research.

[name], Co-Investigator, has conducted research on conjoint and family-involved treatment for individuals for AUDs for more than 40 years. This research has found consistent support for the efficacy of couples approaches in reducing drinking and, in some studies, enhancing relationship stability and satisfaction. She currently is developing a brief family-involved treatment (B-FIT) based on these 3 principles.

Smartphone apps may be useful, convenient, and easily diffusible tools that may extend and strengthen the impact of families on long-term outcomes for DWI offenders.

### 3A.4. Interlock Ignition Device (IID) Research

With the advent of the technology to support the development of IIDs in 1970, these devices have become more sophisticated technologically, allowing digital photography of the driver, WiFi connection to device providers and court systems that allow immediate data transmission of lockout events, and GPS monitoring of driving and breath-testing events. They have also become more widespread in use, with estimates of 300,000 in use among DWI offenders. All 50 U.S. states have some type of IID law, with 25 U.S. states having mandatory IID laws for all DWI offenses. All 50 U.S. states have some type of Ignition Interlock law, with 25 U.S. states having mandatory Ignition Interlock laws for all DWI offenses. Research on the effectiveness of IIDs has shown:

1) IID's reduce the incidence of DWI recidivism while installed in the offender's vehicle, but not once the IID is removed and 2) the frequency of a DWI offender being prevented from starting a vehicle because of a lockout event (the IID sensing the presence of alcohol and disallowing the vehicle to start) predicts DWI recidivism – the more frequent the lockout events, the more likely an offender will have a subsequent DWI arrest. These findings have led researchers to consider ways to extend the effectiveness of IIDs beyond their installation period, including implementing health promotion and treatment programs tied to IID use while in place in offenders' vehicles. Most recently, Voas and colleagues have shown that requiring alcohol treatment of DWI offenders who have frequent IID lockout events resulted in a one-third reduction in DWI recidivism. has recommended increased attention to programs that integrate health promotion interventions while the offender has an IID installed in their vehicle. To date however, no research has examined the impact of family-based treatment on reducing IID lockout events and subsequent DWI recidivism or the provision of family-based treatment via smartphone apps to achieve lockout event reduction and subsequent DWI recidivism. The current investigation will examine this important possibility.

### 3A.5. Summary of Significance

DWI continues to be a major source of injuries and fatalities. To date, DWI interventions have focused almost exclusively on the DWI offender, with little regard for the offender's social environment. Approaches that combine policy-level interventions such as the IID with interventions that target the DWI offender's social environment (e.g., family-focused interventions) are likely to show strong efficacy. We will integrate an effective family-focused brief therapy (B-FIT) with the accessibility of the smartphone to extend the effectiveness of IID, as assessed by IID lockout events, after the device is removed from the vehicle.

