### 3C.6. Randomized Trial Evaluating *B-SMART* (Specific Aim 4; Months 8-24)

**3C.6.1. Experimental Design.** The *B-SMART mobile web app* will be evaluated in a randomized pretest-posttest controlled design. In months 6-11, first time DWI offenders and CFMs will be recruited for participation in the trial. First-time DWI offenders and their CFMs will be randomized together to the intervention (*B-SMART*)

(n=150) or a usual and customary (UC) IID information condition comparison group (n=150) following baseline assessment. Assessment via web-based surveys will be conducted with the DWI offenders and CFMs at baseline, 3-month follow-up, and 9-month follow-up

post randomization. Also, information on frequency of alcohol-positive IID tests (termed “lockout events”) will be acquired by the project from the Santa Fe County and Municipal DWI Program at the 9-month assessment point (posttest only) for each DWI offender. Thus, the proposed efficacy trial (see **Figure 5**) will be a 2 (level of treatment – app intervention vs. UC information) x 3 (level of time – baseline vs. 3-month follow-up vs. 9-month follow-up) mixed factorial design. Baseline and follow-up data collection will be conducted via online surveys and a customized web portal and include DWI offender and CFM alcohol frequency and use measures and measures of family communication and functioning (see 3C.7). Participants will fill out a locator form with contact information and collateral contact information to locate them for assessment at the 3-month and 9-month follow-ups. We have employed these locator procedures in prior trials, keeping average loss across 9 months at 15%-20%. Cumulative IID lockout event data will be collected for all DWI offenders from the Santa Fe County DWI Program at the 9-month assessment point.

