**FIGURE 5: Randomized Efficacy Trial Design**

Time	Experimental Group (randomized)	
	B-SMART Intervention Group N=150 DWI Offenders & CFM	Usual & Customary Information Group N=150 DWI Offenders & CFM
Baseline	study cohort assessment	study cohort assessment
Web App Intervention	YES	NO
3-month Follow-up Post-test	study cohort assessment	study cohort assessment
9-month Follow-up Post-test & IID Data Collection	study cohort assessment	study cohort assessment

**3C.6.2. Recruiting and Consenting Procedures.** Potential participants will be contacted for recruitment and consenting at monthly Santa Fe County DWI Program meetings held for each DWI offender at the beginning of her/his probation period. CFMs of first-time DWI offenders will be contacted via email and a web recruitment portal designed exclusively for the project and followed up with a recruitment phone call.

Participants will only be enrolled in the trial if **both** the DWI offender and CFM consent to participate. Our previous work in Phase I of the project found a strong willingness to participate in the project among both DWI offenders and CFMs based on their interest in better family functioning and the unique convenience of a *B-SMART mobile web app* that could be beneficial to their experiences with the IID.

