## 3C.7. Outcome Measures

**3C.7.1. Measure of Primary Outcome Variable: IID Lockout Events.** The primary outcome

measure will be frequency of IID lockout events from baseline to 9-month follow-up post-randomization, collected from the Santa Fe DWI program database for each first-time DWI offender participant. Marques, Voas and colleagues have demonstrated in a series of investigations that frequency of lockout events strongly predicts DWI recidivism over time, and as such, IID lockout events are an important and useful proxy measure for DWI recidivism. Given the length of time necessary to accumulate DWI recidivism data (average length of time varies across locales and can be between 2 and 8 years), IID lockout events provide a direct and accessible measure of DWI recidivism within the two-year project timeline.

**3C.7.2. Measures of Secondary Outcome Variables and Mediators.** Alcohol use by the DWI offender, a secondary outcome, will be assessed at baseline, 3-month follow-up, and 9-month follow-up with versions of the Form 90 adapted for online assessment for the CFMs (Form 90-ACS) and first-time DWI offenders (Form 90-AF). The Form 90 measures produce detailed quantity and frequency measure of alcohol use for the first-time offender that are validated by the CFM reports. Family functioning will be assessed at baseline, 3-month follow-up, and 9-month follow-up, as potential mediators of *B-SMART* effects, with DWI offenders and CFMs with three measures: (1) Family Environment Scale – Cohesion and Conflict subscales assesses offender and CFM perceptions of positive and negative family functioning; the two subscales selected are strongly associated with treatment outcome; (2) Family Communication Scale from FACES-IV assesses perception of quality of communication in the family; (3) Pleasant Events Schedule (adapted) assesses shared positive activities within a family. These three measures are also being used in the B-FIT study, allowing for comparison of outcomes across the two studies.

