#### DWI Offender:

- male or female
- 21 years or older
- first-time DWI offender with IID installed in vehicle
- enrolled in Santa Fe County DWI Program
- have a smartphone, tablet computer, or personal computer with Internet access
- consent to participate
- able to read and speak English or Spanish

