Four subcommittees will supervise important parts of the project. [name] will chair the Recruitment Committee that will recruit the participating DWI Offenders and CFMs. [name] will be on this committee. Drs. [name] and [name] will co-chair the Intervention Development Committee and will be assisted by [name], [name], and the KB media developers. Drs. [name] and [name] will Co-Chair the Data Collection Committee and survey the DWI Offenders and CFMs and obtain the cumulative IID lockout event data for the DWI offenders from the Santa Fe County DWI Program at the 9-month assessment point. [name], Project Biostatistician, will assist in the development of the procedures for the surveys and lockout event collection. This committee will work to ensure that all data collection procedures have detailed protocols. The Analysis Subcommittee, co-chaired by [name] and [name] with Drs. [name], [name], and [name] and [name] as members, will plan and conduct all data management and analysis procedures. This subcommittee will develop a detailed data analysis plan and supervise work by KB's Biostatistical Manager to prepare all databases for analysis. The subcommittees will meet on a weekly, biweekly or monthly basis as needed depending on the project tasks and activities. Ad hoc committees will be formed to address specialized tasks as necessary. [name] will supervise project activities at KB; [name] will supervise project activities at UNM; and [name] will supervise project activities at Pythagoras, Inc.

The Project Coordinator at KB, [name], will assist [name] with all aspects of the project. [name] will coordinate the relationships among the investigators and project staff, sit on the Steering Committee, and oversee the conduct of the study protocols. [name] (Biostatistical Manager) and [name] (Data Assistant) will perform data management and [name] will assist [name] with day-to-day data analysis tasks. [name] and [name] will create data entry programs for printed forms. [name] and [name] will work with the IRBs to obtain approval of all forms and procedures. [name], [name], and [name] will work together to ensure successful transfer of database files and performance of all analyses.

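### H1 can show only fewer lockouts while the interlock is fitted, not an effect after removal, and the plan names no installed time, removal date, offset or censoring rule for the lockout analyses

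*Combined protocol and SAP*

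**What the plan says.** - **The claim.** Section 3A.5 of the protocol sets out "to extend the effectiveness of IID, as assessed by IID lockout events, after the device is removed from the vehicle".
- **What a lockout is.** Section 3A.4 describes "a lockout event (the IID sensing the presence of alcohol and disallowing the vehicle to start) predicts DWI recidivism". The same section and 3A.1 say that the interlock's benefit is lost once it is taken out.
- **The primary outcome.** Section 3C.7.1 defines it as "frequency of IID lockout events from baseline to 9-month follow-up post-randomization". It justifies the choice by saying that "IID lockout events are an important and useful proxy measure for DWI recidivism", since recidivism takes longer to accumulate than the two-year project allows.
- **Entry.** The eligibility list (2.2) requires a "first-time DWI offender with IID installed in vehicle" and sets no minimum remaining installation time. Recruitment (3C.6.2) takes place at "meetings held for each DWI offender at the beginning of her/his probation period".
- **Data.** Section 3C.6.1 states: "Cumulative IID lockout event data will be collected for all DWI offenders from the Santa Fe County DWI Program at the 9-month assessment point". The SAP adds that the dates of lockouts will be collected. Device dates are not mentioned.
- **Analysis.** In the SAP, H1 is a Poisson regression of lockout events on treatment, with participant as a random effect and a switch to negative binomial if the lockout rates are too skewed. Time to first and later lockouts is supportive, with Kaplan-Meier named. No offset, exposure time or censoring at removal appears.
- **A later plan.** The study-team governance text promises more: "This subcommittee will develop a detailed data analysis plan". The SAP supplied does not contain these items.

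**The concern.** There are two separate points.

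1. **What H1 can support.** Section 3A.5 ties the effect after removal to an outcome that cannot occur after removal. A reader of a positive H1 could take it as evidence that the benefit persists once the interlock is gone, which is the aim the protocol stresses and the claim most useful for commercialisation. The trial would hold no direct evidence on that.

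2. **The denominator.** A 9-month count is comparable between offenders only if each could have had lockouts for the same time. If some devices come out early, the count mixes how often a person is locked out with how long the device was fitted. In a time-to-lockout analysis with no censoring rule, a person whose device is gone could be counted as lockout-free and still at risk. Whether this matters depends on facts the documents do not give, so the plan should collect what is needed to find out.

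**Working it through.** **Point 1: the texts side by side.** Section 3A.4 makes a lockout an act of the fitted device. Section 3A.5 asks lockouts to assess a period when no device is fitted. If every device stays in for 9 months, no time after removal is observed; if some come out, the time after removal contributes no events by construction. Form 90 alcohol use at 9 months could be reported after removal, but it is a secondary outcome, measures drinking rather than driving, and is not what 3A.5 names. This point needs no assumption.

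**Point 2: inputs from the SAP, Sample Size Determination.** Control 4 lockouts per 9 months; two-sided 0.05; 90% power; about a 20% reduction; 119 per group; 15% attrition; 150 randomised per arm. 150 × 0.85 = 127.5, taken as 127.

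*Reproducing the plan's figures.* With mean counts m0 and m1,

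n = (1.960 + 1.282)² × (1/m0 + 1/m1) / [ln(m1/m0)]²

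- 4 against 2.4: 26.8, so 27 (stated 27).
- 4 against 3.2: 10.507 × 0.5625 / 0.04979 = 118.7, so 119 (stated 119).

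The 119 matches an exact 20% reduction. The printed, rounded 0.36 would give 147, which is a separate matter. Both stated sizes use 9 exposed months per person.

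*Shorter installed time.* The mean counts scale with mean installed months T, so n = 118.7 × 9/T. The values of T are assumptions.

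| Mean installed months T | n per group for 90% power |
|---|---|
| 9 | 118.7 |
| 7.5 | 142.4 |
| 6 | 178.0 |

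*Equal removal in both arms (assumed: half removed at month 6, true ratio 0.8).* Mean installed time is 9 − 3 × 0.5 = 7.5 months, with variance 9 × 0.5 × 0.5 = 2.25. The monthly rates are r = 0.444 and 0.356. The per-person variance of the log mean count is as follows.

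- Raw count: (7.5r + 2.25r²)/(7.5r)² = 0.340 (control) + 0.415 (app) = 0.755.
- With offset: 1/(7.5r) = 0.300 + 0.375 = 0.675.

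Power = Φ(0.2231/√(V/n) − 1.960):

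| n per arm | Raw count, V = 0.755 | Offset, V = 0.675 | No removal, V = 0.5625 |
|---|---|---|---|
| 150 | 88.2% | 91.4% | 95.4% |
| 127 | 82.5% | 86.5% | 91.8% |

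Simulation with participant-level (robust) variance agrees to within a point: about 88% to 89% against 92% at 150, and 83% against 87% at 127. Under the null with equal removal the ratio is 1.00, and the raw-count test rejects about 5% of the time with that variance. A Poisson test with no between-participant variance gives 6.1% (30% removed) and 6.5% (50% removed) at 127 per arm.

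*Unequal removal (assumed, at month 6, no app effect on lockouts).* The null ratio of raw counts is the ratio of mean installed times, app over control:

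- 10% control, 20% app: 8.4/8.7 = 0.966.
- 20% control, 40% app: 7.8/8.4 = 0.929.

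In the second case, at 127 per arm, raw counts give false positives of about 19% with participant-level variance (21% without), and 10.8% or 8.2% in a negative binomial model with dispersion 0.5 or 1. With an offset all are about 5%. A wider variance lowers the error rate but leaves the ratio at 0.93.

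**The case against.** Section 3A.5 is background. The operative outcome and H1 refer only to lockouts from baseline to 9 months, and 3C.7.1 openly calls them a proxy, with a reason. That stands: the endpoint choice is declared, and what needs correcting is the wording of the claim.

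No document says that any device is removed before month 9, and recruitment at the start of probation is compatible with all of them staying in. That also stands, and it means every figure for removal is an illustration.

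The SAP uses rate wording, treats participants as a random effect and says the model will account for the temporal design. Participant-level variance does remove the excess false positives under equal removal. It does not define a denominator, and it does not remove bias under unequal removal.

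Lockouts come from program records for all offenders, so survey attrition need not reduce the H1 sample to 127, although withdrawal could, because 3.2.A stops data collection at withdrawal. Both sizes are therefore shown.

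A reader might infer that H1 as planned has a false-positive rate near 20%. The documents do not support that: it needs the app to double early removal while leaving lockouts unchanged. If removal instead followed good performance (simulated: removal at month 6 with at most one lockout, 150 per arm), the null ratio was 1.00, and a true 0.80 appeared as 0.77 to 0.78 raw and 0.80 to 0.81 with an offset. That is a small exaggeration of a real effect.

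**Conclusion.** The point holds in two parts of different strength.

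- **Certain from the text.** H1 cannot measure an effect after removal. It speaks to lockouts while the interlock is installed, and to later recidivism only by proxy.
- **Conditional.** Installed time is undefined in the analysis. With no early removal, the omission is harmless. With equal removal there is no bias and type I error is about 5% under the planned participant-level variance; the cost is precision, 3 to 4 points of power in the 50% illustration. With unequal removal the ratio is biased (0.93 under the null in the illustration), and nothing the plan collects would show it.

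It would be wrong to conclude that the trial is underpowered or that its main test is invalid. Randomisation balances installed time unless the app affects removal, and the documents are silent on both removal and any such effect. This should be changed, but it does not undermine the trial.

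**What to change.** 1. Limit the conclusion from H1, and the wording of 3A.5, to lockouts while the interlock is installed, with recidivism described as reached by proxy.
2. Request installation and removal dates with the 9-month program extract, after confirming that the program holds them.
3. Fit H1 with an offset of log(installed days), counted from randomisation to the earlier of removal or 9 months, in either the Poisson or the negative binomial model.
4. Censor time to first and subsequent lockouts at removal.
5. Report installed time by arm, because an offset does not by itself correct for removal that is tied to lockout performance.

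The cost is two date fields whose availability must be checked, a few lines of SAP text that could go into the promised detailed analysis plan, and a narrower claim.
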